6.2 ENDPOINT AND OTHER NON-SAFETY ASSESSMENTS

The primary outcome will be measured from hospital electronic record (EMR), billing data and/or from the Get With the Guidelines (GWTG) stroke registry data. Data will be separately received from the three hospitals in Flint where patients are sent for EVT (received letters of support and UFA in progress), which together account for 95% of all stroke treatments in Flint residents. The study population will be patients with a primary diagnosis of ischemic stroke using ICD-9 codes and/ or ICD-10 codes^{33, 34}. The primary outcome will be any thrombolysis which includes both IV tPA (MS-DRG 61-63 or ICD-9 procedure code 99.10), intra-artery treatment (MS-DRG 21-23 or CPT codes 37184-6, 37201, 75896) and the combination identified by ICD-9 and ICD-10 codes.³ The research team will attempt to obtain data from 2010 to 2021 if available to account for linear trends (about 6000 ischemic stroke and 8000 total strokes and TIAs). Data will also be obtained from the de-identified publicly available Michigan State Inpatient Database for stroke rates in comparator cities.

Secondary Outcomes: The community secondary outcomes are the number of stroke patients who arrive by ambulance and IV acute stroke treatment rates. Data will be obtained from the EMR. We also request data from the State of Michigan, specifically Michigan Department of Health and Human Services, Michigan EMS Information System UFA (21-UFA04001) or GWTG data of the three hospitals in Flint.

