7.1.1 ANALYSIS OF THE PRIMARY ENDPOINT(S)

The primary analysis will be an interrupted time series comparison of acute stroke treatment rates in the three Flint hospitals. The pre-intervention period will be defined using EMR data prior to the start of the roll out of the community intervention. All patients admitted with a primary diagnosis of ischemic stroke in both the pre-intervention and intervention periods will be included in the primary analysis. Note: process measures evaluating the Stroke Ready campaign (quadrant crossover or music video view IP address) will not be linked to any obtained PHI. Logistic regression will be used to estimate the overall intervention efficacy (indicator variable) in a model predicting receipt of acute stroke treatment (binary variable). If a temporal trend exists in the pre-intervention period, we will adjust for the month since the start of the pre-period as a fixed effect while accounting for clustering at the hospital level. To maximize statistical power, both interventions (hospital-HUM00112536 and all community quadrants-this current protocol) will be parameterized with a single variable. With this approach, statistical power for the primary analysis will be more than adequate. Using hospital administrative and Medicare data, we estimate that at least 480 strokes per year will occur at the 3 Flint hospitals for a total of at least 1,440 strokes in the pre period and 1,800 in the post-period, but to be conservative we are requesting data from 2010 to 2021 about 8000 patients with a stroke. Assuming a doubling in treatment rates (pre-intervention Medicare treatment rate 2.2%),³⁷ we will have over 90% power to detect this difference considering a two-sample binomial difference in proportions. This estimate is consistent with prior simulation work based on ARIMA analyses (effect size of 1.0 (pre-intervention monthly treatment rate = 2.2%, standard deviation = 2.1, predicted post-intervention treatment rate 4.3%, auto-correlation=0.3).³⁸

7.1.2 SECONDARY ANALYSES: REGIONAL COMPARISONS AND QUADRANT-BASED ANALYSES TO ENHANCE CAUSAL INFERENCE

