Secondary analyses will explore the extent that such confounding may influence the primary analysis and enhance the ability to draw causal inferences from the primary analysis. First, we will repeat the primary analysis with a concurrent control group consisting of other large Michigan metropolitan regions (regional control model) where African-Americans make up more than 25% of the population (Detroit, Saginaw, Muskegon, Benton Harbor). This analysis will control for regional effects that may lead to increased treatment rates that occur simultaneously with our intervention in Flint using data from the Michigan State Inpatient Database (SID),³⁹ which collects de-identified data on all acute care hospitalizations in the state of Michigan within a given year. Second, by delivering the intervention sequentially to geographic quadrants within Flint, we will explore whether increases in acute treatment rates parallel the geographic pattern of intervention roll out (geographic model). Specifically, each stroke patient in Flint will be geocoded to one of the four intervention quadrants using EMR data and a geocoding interface. Our primary analysis will then be repeated by modifying the intervention indicator variable to represent whether the intervention was active in the patient's geographic quadrant at the time of intervention.

7.1.3 EXPLORATORY ANALYSES: EFFICACY OF PROGRAM COMPONENTS AND TEMPORAL PATTERNS TO INFORM FUTURE INTERVENTIONS

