To inform future interventions, will also perform a series of hypothesis-generating analyses to inform which elements of the program were most effective and the temporal properties of the program. Due to power concerns, our primary analysis does not consider the difference between the hospital and community effects. Thus, we will first estimate the proportion of the change in the acute stroke treatment rate attributable to the hospital-based intervention vs. the community-based intervention by repeating our geographic model including an indicator variable representing the time period of the hospital intervention as well as a community interaction term. In this way, we will be able to explore whether the Stroke Ready hospital or community based intervention was the most efficacious and whether there was synergy between the interventions. The stepped wedge design is a key innovation to this end. In typical multi-level interventions when all of the elements are rolled out nearly simultaneously, it is impossible to estimate which elements have the highest leverage, however with the stepped wedge design it is possible to gain a greater understanding of which elements are most important. Using simulation analyses, we estimate that there will be 70% power to find a doubling at the community level, 55% power to find a doubling at the hospital level and 21% power to find a doubling through a community-hospital interaction. Because this power is inadequate for a hypothesis-testing evaluation, we have specified this analysis as an exploratory analysis whose purpose is enhance our understanding of the importance of intervention elements and to inform future interventions. Second, we will determine the temporal properties of the Stroke Ready intervention by adding a linear slope term and exploring quadratic terms in our geographic model to estimate the time delay between intervention and changes in treatment rates and whether treatment rates level off or decline as the intervention persists into its latter years. Finally, a strength of our data collection approach is that we will be able to inexpensively assess the sustainability of intervention effect using Michigan SID data years after the intervention is completed without needing to perform additional data collection. Together, such analyses will determine the sustainability of the intervention and inform future interventions.

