7.1.4 ANALYSIS OF THE SECONDARY AND TERTIARY ENDPOINT(S)

Changes in the proportion of patients arriving by ambulance over time will be assessed using logistic regression with an indicator variable representing the intervention period. Changes in IV tPA will be evaluated using an interrupted time series comparison of acute stroke treatment rates in the three Flint hospitals.

Changes in the time from ED presentation to acute stroke treatment and door to treatment will be explored using linear regression with a similar indicator variable representing the intervention period. Changes in outcomes measured with the community survey across intervention waves will be assessed with ordinal logistic regression (Likert-based outcomes) or chi-squared tests (binary outcomes) with indicator variables representing the survey wave. Process and satisfactory measures will be summarized with descriptive statistics, as pre-intervention values will be either unmeasurable or unintelligible, formal statistical comparisons will not be performed.

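### The quadrant roll-out model is planned for treatment receipt only; ambulance arrival, the community outcome closest to the call-911 message, gets only an uncontrolled before-after comparison

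*Combined protocol and SAP*

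**What the plan says.** Section 7.1.2 geocodes each Flint stroke patient to a quadrant and repeats the primary analysis with an indicator for whether the intervention was active there. The question is stated for treatment: "we will explore whether increases in acute treatment rates parallel the geographic pattern of intervention roll out". The extensions in 7.1.3 (hospital term, interaction, slope and quadratic terms) also concern treatment rates. For the component analysis 7.1.3 reports that "there will be 70% power to find a doubling at the community level" and calls the power too low for hypothesis testing.

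Section 6.2 states: "The community secondary outcomes are the number of stroke patients who arrive by ambulance", together with the IV treatment rate. Table 2 gives the ambulance outcome the goal of optimising the community, with the Flint hospitals as its source. Under 7.1.4, the change in the ambulance proportion "will be assessed using logistic regression with an indicator variable representing the intervention period". No quadrant term, time term or comparison region is mentioned for it.

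**The concern.** The staggered roll-out is the only comparison inside Flint that can separate the community activities from city-wide change. The plan uses it on an outcome that few patients have and that also depends on what happens after arrival. Ambulance arrival comes earlier in the causal chain, and calling 911 is part of the core workshop content and the action plan in section 4.1. Aim 3 asks about the relative importance of the two arms and about the processes that mediate the outcome.

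As written, the ambulance result is a plain before-after contrast. It is open to the same time-related confounding that 7.1.2 was added to address for treatment. If the quadrant treatment model shows nothing, the reader cannot tell a campaign that left 911 use unchanged from a test with too little information. If the ambulance model is added after results are known, it will be post hoc.

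**Working it through.** **Inputs from the documents (7.1.1 and 4.2).** Volume: "we estimate that at least 480 strokes per year will occur at the 3 Flint hospitals". Sample: "at least 1,440 strokes in the pre period and 1,800 in the post-period". Effect: "Assuming a doubling in treatment rates (pre-intervention Medicare treatment rate 2.2"%), or in the ARIMA sentence "predicted post-intervention treatment rate 4.3%, auto-correlation=0.3". There are four quadrants with 6-month steps.

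**Assumptions.** Two-sided 5% test; strokes split evenly, so 480/12/4 = 10 per quadrant per month; hence 1,440/40 = 36 months before and 1,800/40 = 45 months after; ambulance share 30-60%; intervention indicator on from each quadrant's start onward.

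**The plan's own figure.** Two-sample binomial power with 1,440 and 1,800 strokes is 93.6% for 2.2% against 4.4%, and 91.7% for 2.2% against 4.3%. The stated figure of over 90% reproduces. The 70% community figure cannot be checked because its simulation inputs are not given. For a doubling, and without a hospital term, my approximations to the geographic model give 76-93% with no time term, 38-43% with a linear month term and 26-28% with 6-month steps. The ranges cover 24 or 45 months of post-period.

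**Why the outcome matters.** In a logistic model the SE of the log odds ratio is proportional to 1/√[n p(1−p)]. For the same records the ratio of treatment SE to ambulance SE is √[pA(1−pA) / pT(1−pT)]. With pT = 0.022, pT(1−pT) = 0.0215.
- pA = 0.30: √(0.21/0.0215) = 3.1
- pA = 0.50: √(0.25/0.0215) = 3.4

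If treatment doubles, its SE shrinks and the ratio falls.

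**Model-based check.** I took the Fisher information of a logistic model on expected counts by month and quadrant, with quadrant terms, for a treatment doubling and an ambulance odds ratio of 1.5. The detectable odds ratio at 80% power is exp(2.8 × SE), where 2.8 = 1.96 + 0.84.

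| Time adjustment | SE, treatment | SE, ambulance | Detectable OR, ambulance |
|---|---|---|---|
| None | 0.21 | 0.072-0.076 | 1.22-1.24 |
| Linear month | 0.40 | 0.136-0.144 | 1.46-1.50 |
| 6-month steps | 0.52 | 0.178-0.187 | 1.65-1.69 |
| 6-month steps, half the strokes geocoded | 0.73 | 0.25-0.27 | 2.0-2.1 |

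The SE ratio is about 2.8 to 2.9 in every row. It falls to about 2.7 at a 60% share if the ambulance odds ratio is 2. Ending follow-up at the 24-month roll-out gives detectable odds ratios of about 1.5 (linear) and 1.7 (steps).

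From a 45% share (odds 0.818), an odds ratio of 1.5 means 55% and 1.7 means 58%. For treatment the detectable odds ratio is exp(2.8 × 0.40) = 3.1 with a linear month term and exp(2.8 × 0.52) = 4.3 with steps.

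**What precision does not settle.** Ambulance arrival has more power than a treatment doubling only if its own odds ratio exceeds exp(ln 2 / 2.8) = 1.28.

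**Effect of only four clusters.** Suppose quadrant-by-period variation adds 0.2 on the log-odds scale to both outcomes (illustrative). The SEs with steps become √(0.52² + 0.2²) = 0.56 and √(0.185² + 0.2²) = 0.27, a ratio of about 2.0.

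**The case against.** Section 7.1.2 says its purpose is to strengthen causal inference from the primary analysis, so using the primary outcome is a deliberate choice. That stands: the plan contains no error here, and the treatment model should stay. The choice does not prevent fitting the same model to a second outcome.

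A smaller standard error is not the same as more power. The documents give no expected ambulance effect, and on the risk-difference scale the ambulance standard error is the larger one (2.7 to 3.4 times). This also stands. The precision claim belongs to the log-odds scale, which is the plan's model for both outcomes.

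A reader might infer from the plan's 70% figure that an ambulance odds ratio near 1.3 is detectable: ln 2/(1.96 + 0.524) = 0.279, divided by 2.8, gives exp(2.8 × 0.0996) = 1.3. That step joins a simulation with undisclosed inputs, for a model with hospital and interaction terms, to an SE ratio from a different model. The documents do not support it.

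A reader might also infer that this would be the main test of whether the community arm worked. Table 1 puts radio, TV and internet in every quadrant from Time 1, and section 5.3 allows workshops outside the active quadrant. The contrast therefore captures only the workshop, mailer and print increment, and that in diluted form. The same dilution affects the planned treatment model, so it is no reason to prefer treatment alone.

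Independence of ambulance arrival from the hospital intervention cannot be confirmed, because that intervention is under a separate approval. Completeness of arrival mode is not stated; section 6.2 names hospital records and also state EMS or registry data.

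**Conclusion.** The point holds as a worthwhile, low-cost addition to the plan. Sections 7.1.2 to 7.1.4 contain no quadrant-level analysis of ambulance arrival, and its planned analysis has no internal control. The gain in precision is roughly 2.7 to 2.9 times on the log-odds scale for shares of 30-60%. Even so, the ambulance analysis would detect only moderate to large effects: odds ratios of about 1.5 to 1.7, or 2.0 to 2.1 with steps if half the strokes geocode.

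These figures are best case. They rest on an assumed ambulance share, even quadrants, complete arrival mode and no extra variation between quadrants over time. They do not show that the ambulance analysis would be well powered for the effect that will occur, and they do not touch the validity of the primary analysis.

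**What to change.** In 7.1.2, with a cross-reference in 7.1.4, pre-specify that the geographic model will also be fitted with ambulance arrival (yes or no for each geocoded Flint stroke patient). It should use the quadrant-specific intervention indicator, quadrant terms and the same time adjustment as the treatment version. Report the two side by side, with ambulance arrival as a supportive quadrant-level analysis of the community component and not ranked above treatment.

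State that it estimates the workshop, mailer and print increment over city-wide media, not the whole campaign. Name the source of arrival mode and report its completeness by hospital and period.

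The cost is one more model on data already requested, some added wording, and one more secondary comparison to interpret. No new patients are needed.

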1.2 SCHEDULE OF ACTIVITIES

Table 1: Stroke Ready Community Intervention Timeline

Quad	Time 0	Time 1	Time 2	Time 3	Time 4
1	Pre-Intervention	Workshop/Mailer Media: Radio/TV/Internet Poster/Brochure	Media: Radio/TV/Internet Poster/Brochure	Media: Radio/TV/Internet Poster/Brochure	Media: Radio/TV/Internet Poster/Brochure
2	Pre-Intervention	Media: Radio/TV/Internet	Workshop/Mailer Media: Radio/TV/Internet Poster/Brochure	Media: Radio/TV/Internet Poster/Brochure	Media: Radio/TV/Internet Poster/Brochure
3	Pre-Intervention	Media: Radio/TV/Internet	Media: Radio/TV/Internet	Workshop/Mailer Media: Radio/TV/Internet Poster/Brochure	Media: Radio/TV/Internet Poster/Brochure
4	Pre-Intervention	Media: Radio/TV/Internet	Media: Radio/TV/Internet	Media: Radio/TV/Internet	Workshop/Mailer Media: Radio/TV/Internet Poster/Brochure

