4 STUDY DESIGN

4.1 OVERALL DESIGN

The Stroke Ready project is a quasi-experimental, health behavior theory based, hospital and community behavioral intervention designed to increase acute stroke treatments. The community intervention will be sequentially delivered to each Flint quadrant, i.e. four clusters defined by the community's geographic boundaries, until all the quadrants have crossed over from control to intervention eventually reaching the entire community (Table 1). This strategy will allow the research team to observe the effects of the community intervention separately from the hospital intervention (HUM112536) to assess the impact of each intervention level. The community intervention consists of workshops, mailers, print, radio and internet media. (Details on study components are in the *Intervention Components* section of this protocol.)

The community intervention components focus on public health education emphasizing the significance of stroke preparedness. Primary Stroke Ready components will consist of peer facilitated educational workshops, a music video adapted and expanded from the pilot (HUM98718), a mass media campaign including print materials (e.g. posters, brochure), health promotion mailers, radio/TV public health service announcements, and the Stroke Ready website and Facebook page (Table 3). The community intervention components are purely public health education, which includes stroke knowledge and stroke preparedness education, and were piloted in (HUM00098718). With regard to the music video, educational print materials, internet platforms, and mailers, there is no need to actively recruit as these interventions will be distributed and/ or implemented among the community as the others parts of the public health stroke preparedness message. We anticipate reaching about 5000 people.

Table 3: Overview of Stroke Ready Components

Intervention components	Summary of intervention	Behavioral Construct	Focus Population	Delivery
Peer-led Workshop	Discussion and interactive stations	self-efficacy, attitude, social norms, knowledge	Churches, organizations, businesses	Peer leaders
Music Video	Educational music video of stroke preparedness	self-efficacy, attitude, social norms, knowledge	Churches, organizations, businesses, events	Peer leaders, local broadcasting station, social media, website

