5.3 STRATEGIES FOR RECRUITMENT AND RETENTION

The research team and Stroke Ready peer-leaders will work together to recruit organizations and participants for the Stroke Ready workshops through recruitment announcements, flyers, internet platforms, and word-of-mouth. Additionally, the research team or peer leaders may provide a courtesy reminder call several days before the workshop. Since Flint is naturally divided into 4 quadrants the study team will select each quadrant for implementation and then for about the next 6 months they will focus their workshop recruitment efforts and material dissemination on the selected quadrant of the city. However, given the commitment to CBPR the quadrant implementation is preferred but we would not forego a workshop in a quadrant that we are not focusing on at the time if requested. During this time the research team and community partners, including peer leaders, will work together to implement the Stroke Ready workshops and distribute educational posters and materials. At the end of about six months, the materials will remain in the quadrant and efforts will shift to the next quadrant for recruitment and workshop delivery.

To overcome challenges of recruiting racial minorities, low-income individuals, and other disadvantaged populations due to lack of transportation, childcare, inconvenient hours, etc., the research team designed the workshops such that participants can participate at their convenience. The workshops are voluntary and will be delivered by peer-leaders at locations during times that are convenient for the community (e.g. after church services, during lunch breaks). Additional factors that facilitate program recruitment and participation are: 1) the workshops, as well as all Stroke Ready materials and activities, are free and have no more than minimal risk; 2) recruitment materials and intervention components were created by the community for the community; 3) the research team has gained support of local leadership and

community members with strong ties in the Flint community; 4) children will be allowed to attend (HUM00098718).

Internet platforms will be utilized to recruit participants. Upcoming workshop events will be posted on the Stroke Ready Facebook page and website.

The research team will oversee the activities related to workshop participant recruitment to track the campaign's reach and resources, and workshop delivery processes to assess workshop fidelity.

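### The secondary geographic model has no quadrant effects and only conditional calendar-time adjustment, so citywide change can pass for a roll-out effect

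*Combined protocol and SAP*

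**What the plan says.** Section 7.1.1 sets the primary model: "Logistic regression will be used to estimate the overall intervention efficacy (indicator variable) in a model predicting receipt of acute stroke treatment". Calendar time enters conditionally: "If a temporal trend exists in the pre-intervention period, we will adjust for the month", as a fixed effect, "while accounting for clustering at the hospital level". No criterion is given for deciding that a trend exists.

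Section 7.1.2 then defines the geographic model: "Our primary analysis will then be repeated by modifying the intervention indicator variable to represent whether the intervention was active" in the patient's quadrant. Sections 7.1.1 to 7.1.3 specify no quadrant or calendar-period effects. Section 7.1.3 adds a hospital-period indicator, an interaction, and slope or quadratic terms, but only in exploratory extensions. For one of these it says "we estimate that there will be 70% power to find a doubling at the community level".

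On exposure, section 4.1 describes sequential delivery "until all the quadrants have crossed over from control to intervention" and lists radio and internet media among the intervention's components. Table 1 (section 1.2) enters "Media: Radio/TV/Internet" for quadrants 2 to 4 from Time 1, before each quadrant's own workshop and mailer step. Section 5.3 adds that "we would not forego a workshop in a quadrant that we are not focusing on at the time if requested".

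**The concern.** In a stepped roll-out the share of quadrants that have crossed over rises with calendar time by design. Anything that changes citywide (a secular trend, the hospital intervention, the media campaign) is therefore correlated with the quadrant indicator. The usual protection is to compare quadrants within the same period and to let each quadrant have its own baseline. The text requires neither.

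Section 7.1.2 offers this model as a check on confounding in the primary analysis. Without those terms it tends to confirm a confounded primary result. The same model carries the hospital-versus-community split in section 7.1.3, which supplies the separate effect sizes for the cost-effectiveness analysis in section 7.1.5.

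**Working it through.** **Inputs from the documents.** At least 480 strokes a year (40 a month); 1,440 pre and 1,800 post; 2.2% doubling to 4.4% (section 7.1.1). Four six-month steps (Table 1, section 4.2). 1,440/40 = 36 pre-months. The post-period is 24 months by Table 1 and the synopsis, or 1,800/40 = 45 months by section 7.1.1; both are shown.

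**Assumptions.** Equal quadrants (10 strokes per quadrant-month), every stroke geocoded to a Flint quadrant (optimistic), no extra hospital-level variance, two-sided 5% (alpha is not stated).

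**The plan's own figure.** For the primary comparison, pooled p = (31.68 + 79.2)/3,240 = 0.0342; null SE 0.00643; alternative SE 0.00619. Power = Φ[(0.022 − 1.96 × 0.00643)/0.00619] = Φ(1.52) ≈ 93.6%. The stated figure of over 90% reproduces. No power is stated for the geographic model itself.

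**Indicator only, citywide doubling at launch, no local effect.** Quadrants 2, 3 and 4 wait 6 + 12 + 18 = 36 quadrant-months, or 360 strokes, scored 0.
- Rate when scored 0: (1,440 × 0.022 + 360 × 0.044)/1,800 = 47.52/1,800 = 2.64%.
- Rate when scored 1: 4.4%.
- OR = (0.044/0.956)/(0.0264/0.9736) = 1.70, where the true local OR is 1.
- 24 months (600 strokes scored 1): SE = √(1/26.4 + 1/573.6 + 1/47.52 + 1/1,752.48) = 0.247; z = 2.14; rejection 57%.
- 45 months (1,440 scored 1): SE 0.195; z = 2.71; rejection 77%.

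**Indicator only, media effect of OR 1.5.** The post-launch rate is 3.26%. The rate when scored 0 is (31.68 + 11.75)/1,800 = 2.41%, so OR = 1.36.

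**All three scenarios.** Large-sample logistic fits to the expected rates; entries are OR and rejection rate for 24 / 45 post-months.

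| No local effect | Indicator only | Indicator + month | Quadrant + period |
|---|---|---|---|
| Growth OR 1.10 per year | 1.24 (13%) / 1.36 (33%) | 1.00 (5%) / 1.00 (5%) | 1.00 (5%) |
| Media OR 1.5 | 1.36 (20%) / 1.36 (31%) | 1.08 (5%) / 1.10 (6%) | 1.00 (5%) |
| Citywide or hospital doubling | 1.70 (57%) / 1.70 (77%) | 1.10 (6%) / 1.17 (7%) | 1.00 (5%) |

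**Would the month term enter?** A step at launch leaves the pre-period flat, so it triggers adjustment only by chance. For growth of OR 1.10 per year, ln 1.10 = 0.095 with SE 0.194 in 1,440 pre-period strokes, so z = 0.49. If existence of a trend means p < 0.05 (an assumption), it is detected about 8% of the time.

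**Quadrant baselines.** Section 2.2 says the best areas of Flint reach the national average of 4.2% against a Flint mean of 2.2%. Take baselines of 1.1%, 2.2%, 2.2% and 4.2% (assumed), no effect, and 24 post-months. The null OR then runs from 0.75 to 1.28 with the indicator only, and from 0.60 to 1.69 with month, depending on quadrant order. Period effects without quadrant effects give 0.45 to 2.25. Adding quadrant effects returns 1.00.

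**Cost in power.** A doubling is OR 2.05, ln = 0.716.
- Quadrant + period effects: SE 0.544 / 0.518, z = 1.32 / 1.38, power 26% / 28%.
- Quadrant + month + citywide post-launch term: SE 0.465 / 0.444, z = 1.54 / 1.61, power 34% / 36%.
- Indicator only: 80% / 94%. Indicator + month: 44% / 47%.

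With period effects the information comes from Times 1 to 3: 3 × 6 × 40 = 720 strokes, 360 in each state, and 360 × 0.022 + 360 × 0.044 ≈ 24 treated patients.

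**What the adjusted coefficient means.** If media carries half of a true doubling on the log-odds scale, the quadrant + period model returns OR 1.43. If media carries all of it, the model returns 1.00. It estimates the local increment over media.

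**The case against.** The strongest reply has four parts.

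- **The plan does provide for time.** In the three scenarios above, a single linear month term brings rejection down to 5–7%. This stands: the large errors belong to the indicator-only branch, and a reader should not infer that the plan always produces them. What remains is that the branch is chosen by an unspecified pre-period check that would usually miss a modest trend and is not designed to see a step at launch.
- **The analysis is secondary.** Section 7.1.2 frames it as exploration, and section 7.1.3 calls its own power inadequate for hypothesis testing. The regional control model in section 7.1.2 also addresses secular change shared with other Michigan cities. This stands and limits the severity. That model does not, however, remove Flint-only change such as local media or the hospital intervention.
- **The media coding is not written down.** A reader might infer that the plan states that media-only quadrants are controls in this model. It does not; it leaves active undefined. The coding is inferred because the alternative, counting media as active, would switch on every quadrant at Time 1 and leave no geographic contrast.
- **The 70% cannot be called wrong.** A reader might set 26–36% against it and conclude that it is overstated. It belongs to the extension with hospital and interaction terms, and its simulation inputs are not given, so the two figures are not like for like.

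The 36 pre-months are also only one reading, since data from 2010 are requested. With 96 pre-months a trend test would detect growth of OR 1.10 per year about two-thirds of the time, but the indicator-only error would rise.

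**Conclusion.** The point holds for the secondary geographic model and its exploratory extension. As written, citywide change can appear as a geographic pattern. With no local effect, the indicator-only branch gives OR 1.24 to 1.70 and rejects 13% to 77% of the time, depending on the scenario and the length of the post-period. The month branch cuts this to OR 1.00–1.17 and 5–7%. It is not guaranteed to be used, and it leaves null ORs of up to about 1.7 under the assumed quadrant baselines.

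These sizes rest on equal quadrants, full geocoding, 36 pre-months and the illustrative effect sizes. The doubling at launch is a deliberately large case, since the documents here do not give the timing of the hospital intervention.

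It would be wrong to infer that the primary estimate is affected; it does not use this model. The change should be made before analysis, but it is not a condition for the primary result.

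**What to change.** In section 7.1.2:

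1. Require quadrant fixed effects and unconditional calendar time, using either (a) period fixed effects or (b) linear month plus a citywide post-launch (media) indicator. Do not combine period effects with a media level: media starts in every quadrant at Time 1, so the two are collinear.
2. Define active as local workshop, mailer or print activity begun in the patient's quadrant by the date of the stroke. Section 7.1.2 currently refers to the time of intervention. Describe the coefficient as the increment of local components over citywide media.
3. Log off-schedule workshops and add a sensitivity analysis that recodes those quadrant-months.
4. Reconcile the note in section 7.1.1 that quadrant crossover will not be linked to PHI with the geocoding of patients to quadrants in section 7.1.2.

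In section 7.1.3, carry the same terms into the extension, recompute the 70% community power under that model, and state the simulation inputs.

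The cost is protocol wording and a few model terms; addresses, hospital dates and the roll-out schedule are already planned. The real price is precision: a wider interval and probably a lower stated exploratory power. The result is best reported as an estimate with its confidence interval.
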